13.1.1. Derivation Cohort Sample Size

The size of the derivation cohort has been calculated to provide at least 10 events per variable that we expect to enter into the logistic regression model. Recording at least 120 RD events would allow around 12 predictor variables to be entered into logistic regression. Assuming an incidence of 12% of subjects with RD episodes and 12-variables for prediction rule, a sample size of 1000 subjects is needed for the derivation cohort.

The selection of 12 high risk variables for the prediction rule has been based on literature review^{1,4,7,16,17,22}:

- Age > 65 y.
- Known or suspected sleep-disordered breathing (OSA, snoring, etc.).
- High risk surgery \leq 24 hours.
- PCA or epidural or intrathecal therapy.
- Obese (BMI >30).
- Multiple opioid or concurrent CNS/sedating medication (benzodiazepines, sleep aids, muscle relaxant, etc.).
- High opioid dosage (>30mg oral morphine per day or equivalent).
- Major organ failure.
- Diabetes.
- Chronic heart failure or other significant cardiac disease.
- Smoke (> 20 packs per year).

Version 3.0, 29 Nov 2016

PRODIGY CIP

- COPD or other significant pulmonary disease (including respiratory events before ward admittance).

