13.3. Primary Endpoint

At the end of data collection all subjects enrolled will be randomly assigned to the derivation set and the validation set at a ratio of 2 to 1. According to the outcome of the planned RD event rate monitoring, there could be the possibility to use the overall population as the derivation cohort. The validation sets will be performed using a bootstrapping method. A detailed description of the bootstrap method will be

Version 3.0, 29 Nov 2016

PRODIGY CIP

reported in the Statistical Analysis Plan (SAP). Bivariate odds ratios (ORs) and 95% confidence intervals (95% CIs) will be estimated. The possibility of collinearity between categorical variables will be also tested. The logistic regression model will be performed using a backward stepwise selection procedure in which the presence of event will be the dependent variable. Independent predictors will be entered into the model if a significant association, defined as $p \le 0.05$, will be identified from bivariate analysis and, to avoid over-fitted and unstable model the correlation coefficient between them should be less than 0.25.

The predictive risk score for RD will be calculated by multiplying each b coefficient (from the multivariate model by 10 and rounding to the nearest integer. The integers will then be added together to produce an overall RD risk score for each subject. The resulting continuous distribution of total risk scores across all subjects in the derivation set will be then stratified into 3 categories of points that grouped subjects according to the level of risk (low, medium and high risks). Model prediction performance will be assessed using calibration (the agreement between predicted and observed outcome) and discrimination (the ability to separate subjects with and without the outcome) and the R2 will be reported as an overall measure for discrimination and calibration. The Sensitivity and Specificity and the receiver-operating characteristic (ROC) curves will be used to visualize the overall accuracy of the model. The discriminatory performance of the model will be validated by comparing the ROC curve analysis in the derivation set with that in the validation set.

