7.10.1.1 Deriving the model

Note for Programmer: The analysis for the primary objective will be performed on a Dataset with one row per patient with RD episode as validated by CEC as the dependent variable (at least one RD) and baseline predictors as independent variables. Potential predictors will be reported on continuous scale or grouped into categories.

The logistic model will be used for bivariate e multivariate odds ratios (ORs) and 95% confidence intervals (95% CIs) will be estimated for each potential predictor. The following steps will be followed to derive the score for each predictor according to categories⁴:

- Determine categories for each risk factors (the most will be 0/1)
- Determine reference class for each risk factor (for dummy the reference category is 0)
- Calculate mid-values to represent categories
- Determine multiplier β
- Determine point score for each risk factor category

If **Data Split** approach:

- Repeat multivariate model on the validation set
- Calculate performance measures
- The "Optimism" is the difference between the performance measures from validation and derivation set

If **Bootstrapping** approach:

- 500 bootstrapped replications of the multivariate model

- Calculate performance measures bootstrapped
- The difference between the bootstrapped performance and the model performance will be averaged to obtain an estimation of the “optimism” of the model. The optimism will be used to validate the model.

Table 25 - RD Risk Score Derivation identified by logistic – MFAS

Predictors	Bivariate analysis OR (95% CI) (N=XXXX)	Multivariate analysis OR (95% CI) (N=XXXX)	Coefficient	Adjusted Coefficient	Risk score point
Char#1	x.xx (x.xx- x.xx)	x.xx (x.xx- x.xx)	x.xxx	x.xx (x.xx- x.xx)	xx
Char#2	x.xx (x.xx- x.xx)	x.xx (x.xx- x.xx)	x.xxx	x.xx (x.xx- x.xx)	xx
...					
Char#N	x.xx (x.xx- x.xx)	x.xx (x.xx- x.xx)	x.xxx	x.xx (x.xx- x.xx)	xx

The collinearity between categorical variables will be also tested by means the Cramer V test for nominal variables and Kendal’s tau-b for ordinal variables. The multivariate logistic regression model will be performed using a stepwise selection procedure in which the presence of event will be the dependent variable. Independent predictors will be entered in to the model if a significant association, defined as $p \leq 0.05$, will be identified from bivariate analysis and, to avoid over-fitted and unstable model the correlation coefficient between them should be less than 0.25.

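### The 0.25 correlation limit on predictors gives almost no model stability and can exclude genuine RD risk factors from the score

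*SAP*

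**What the plan says.** SAP 7.10.1.1 sets two conditions for entry to the multivariable logistic model. The first is a bivariate screen at p ≤ 0.05: "Independent predictors will be entered in to the model if a significant association" is found. The second is that "to avoid over-fitted and unstable model the correlation coefficient between them should be less than 0.25". Protocol 13.3 has the same pair of conditions, with the "correlation coefficient between them should be less than 0.25". After entry, the protocol plans backward stepwise selection; the SAP says only stepwise.

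The SAP also names the association measures: "The collinearity between categorical variables will be also tested by means the Cramer V test for nominal variables", and Kendall's tau-b for ordinal ones. It expects mainly binary predictors: "Determine categories for each risk factors (the most will be 0/1". The candidates are the 12 risk factors in protocol 13.1.1, where "The selection of 12 high risk variables for the prediction rule has been based on literature review". The points of the score are the coefficients of the final model times 10, rounded.

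Neither document gives a reason for the value 0.25, reports a correlation or prevalence for any candidate, plans a VIF or tolerance check, or says which member of a correlated pair is dropped.

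**The concern.** The limit is meant to prevent over-fitting and instability, but it sits far below the level at which correlation between predictors causes either. It also acts directly on the primary deliverable, because it helps decide which risk factors are in the score. If two candidates are both predictive and moderately correlated, one can be shut out although both passed the screen, and the score then discriminates less well than it could. Because the choice of which one goes is left open, two analysts following the SAP could produce different scores from the same data.

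**Working it through.** **1. The plan's own size.** From protocol 13.1.1 and 13.1.2: 12 predictors × 10 events = 120 RD events; 120/0.12 = 1000 derivation subjects; 1000/(2/3) = 1500; 1500 × 1.10 = 1650. The figures reproduce. By the plan's own rule, over-fitting is handled by events per variable, and that allowance already covers all 12 candidates: "Recording at least 120 RD events would allow around 12 predictor variables to be entered into logistic regression".

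**2. What 0.25 means for stability.** For two predictors, VIF = 1/(1 − r²), and the standard error grows by √VIF. For 12 predictors all correlated pairwise at r, VIF = (1 + 10r)/((1 − r)(1 + 11r)).

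| r | VIF, two predictors | SE increase | VIF, all 12 at r |
|---|---|---|---|
| 0.25 | 1.07 | 3.3% | 1.24 |
| 0.50 | 1.33 | 15% | 1.85 |
| 0.80 | 2.78 | 67% | 4.59 |

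Read the other way, a VIF of 5 between two predictors needs r = √(1 − 1/5) = 0.89.

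A simulation agrees. Taken from the plan: n = 1000 and 12% RD. Assumed: two 0/1 predictors, 35% prevalence each, true odds ratio 2 each (β = 0.693). With both kept, the mean β is 0.685 at correlation 0.25 and 0.692 at 0.5. The SE is 0.205 and 0.231, against 0.199 with no correlation.

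**3. How easily the limit is reached.** For two 0/1 variables, Cramér's V equals |phi|. I take V as the coefficient to which 0.25 applies; the SAP implies this but does not say it outright. With prevalences p and q, the joint probability is p₁₁ = pq + phi·√(p(1−p)q(1−q)), and OR = p₁₁p₀₀/(p₁₀p₀₁). At phi = 0.25:

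- 50%/50%: OR 2.8
- 30%/30%: p₁₁ = 0.09 + 0.25 × 0.21 = 0.1425, so OR = (0.1425 × 0.5425)/(0.1575²) = 3.1
- 25%/10%: OR 5.0
- 35%/8%: OR 6.7

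The prevalences are illustrative. Pairs on the plan's list that could plausibly reach these values are obesity with sleep-disordered breathing, age with cardiac disease, and opioid dose with multiple opioid or sedating drugs. That is judgement, not data from the documents.

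**4. Noise at the cut.** With 35% prevalences and n = 1000, the SD of a sample correlation is about 0.03. A true 0.22 breaches the limit in about 17% of samples; a true 0.28 breaches it in about 83%. Near the limit, exclusion is partly chance, and it could differ between the bootstrap replications of SAP 9.2.

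**5. Cost to the score under the planned sequence.** Assumed: all 12 predictors genuine, prevalences 8–40%, five pairs at phi 0.28–0.33, and the member with the smaller p-value kept. Taken from the plan: n = 1000, 12% RD, p ≤ 0.05 screen, then stepwise selection. The loss is the drop in c-statistic caused by adding the 0.25 limit.

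| True odds ratios | Extra loss in c-statistic, across runs |
|---|---|
| 1.2–1.5 | about 0.002 |
| 1.5–1.8 | 0.012–0.019 |
| 1.8–2.2 | 0.026–0.034 |

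In one run the c-statistic went from 0.591 to 0.589 and the mean number of predictors from 3.6 to 3.4 (odds ratios 1.2–1.5); with odds ratios 1.5–1.8 they went from 0.673 to 0.661 and from 6.4 to 5.0. With only one pair above the limit (phi 0.27), the loss was 0.001–0.002.

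**The case against.** The best defence is that this is a conservative parsimony rule, stated in advance in both documents, for a study that wants a simple tool. It is worded as something that should hold, it uses correlations among predictors rather than outcomes, and the performance of the final score is reported in validation whatever the rule does. With weak predictors the screen and stepwise steps cost far more than this limit: 0.031 against 0.002 in the run with odds ratios 1.2–1.5. Any replacement, such as VIF > 5, is also a convention. All of this stands, and it limits the severity. It does not rescue the stated purpose: a VIF of 1.07 is not instability, and parsimony is not the reason the documents give.

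Three stronger readings are tempting but not supported.

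- **That genuine risk factors will be thrown out.** No correlation is reported, so no pair is known to exceed 0.25. Applying the limit to all 12 candidates without the screen and stepwise steps gives losses of 0.013–0.030, but that is not the planned analysis and overstates the limit's own effect.
- **That the retained factor's points become biased.** In the two-predictor simulation with correlation 0.25, dropping one factor moves the other's odds ratio from 2.0 to 2.36 and its points from 7 to 9. For a prediction score, that is the right coefficient for the reduced model. The cost is lost discrimination, not miscalibration.
- **That STOP-BANG will collide with its own components.** SAP 7.6 derives it, but it is not among the 12 predictors in protocol 13.1.1, and neither document says that it enters the model.

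**Conclusion.** The point holds in conditional form. That the limit gives almost no stability is arithmetic and needs no assumption about the data. That it can exclude genuine, already screened predictors follows from the rule as written. How much this costs rests on assumed correlations, prevalences and effect sizes: about 0.002 in c-statistic with modest effects, 0.01–0.03 with stronger ones, and close to nothing if few pairs exceed 0.25. The missing rule on which member of a pair is dropped is a gap in pre-specification whatever the correlations turn out to be. This should be fixed before the model is derived; it does not invalidate the study.

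**What to change.** In protocol 13.3 and SAP 7.10.1.1:

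- Delete the condition that the correlation be below 0.25.
- Assess collinearity by VIF or tolerance in the multivariable model.
- Act only on real redundancy, for example VIF > 5, and state the chosen value as a convention.
- Name in advance which member of a redundant pair is kept.

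The cost is about one sentence in each document. No new data are needed, and the planned 120 events, 1000 derivation subjects and 1650 in total do not change, since they already allow for 12 predictors. The downside is a score that may keep one or two more items.

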7.6 Derived variables

The statistical evaluations will use some derived variables as listed below. All additional derived variables or changes on the variable listed below are reported in the Statistical Programming Requirements document.

New Variables	Derivation
Monitoring Exposure (minutes)	End monitoring date/time – Start monitoring date/time
Study Exposure (days)	(Study Exit date – date of enrollment)/30.44
BMI35	If BMI >35 then BMI35=1 otherwise BMI35=0
Obese	If BMI >30 then Obese=1 otherwise Obese=0
AGE50	If Age >50 then AGE50=1 otherwise AGE50=0
AGE65	If Age >65 then AGE65=1 otherwise AGE65=0
STOP BANG SCORE	The score is the sum of the following points for each patient: If Snoring loudly= Yes then add 1 point If Tiredness in daytime= Yes then add 1 point If Observed apnea during sleep= Yes then add 1 point If Treated for High blood Pressure= Yes then add 1 point If Body mass index >35 (kg/m2) then add 1 point If Age >50 years then add 1 point If Neck circumference >40 cm (16 inches/17inches according to gender) then add If Gender = Male then add 1 point
Opioids Tolerant §	The FDA definition will be used: A patient is considered opioid tolerant if for at least 1 week he/she has been receiving one of the following: 
 • 60 mg oral morphine/day • 25 mcg transdermal fentanyl/hour • 30 mg oral oxycodone/day • 60 mg oral hydrocodone/day • 8 mg oral hydromorphone/day • 25 mg oral oxymorphone/day • Equi-analgesic dose of any other opioid The Morphine Milligrams Equivalent will be used.
STOP BANG SCORE Class	If 0≤STOP-BANG score ≤2 then STOP BANG SCORE Class= 1 labeled as “Low risk of OSA” If 3≤STOP-BANG score ≤4 then STOP BANG SCORE Class= 2 labeled as “Intermediate risk of OSA” If 5≤STOP-BANG score ≤8 then STOP BANG SCORE Class= 3 labeled as “High risk of OSA”
High Risk Surgery	If occurred within 24 hours
Known or suspected sleep-disordered breathing§	if “Yes to OSA (from Medical History) + YES to first 4 questions of the Apnea History
PCA or epidural or intrathecal therapy	PCA with route as epidural or intrathecal from CM
Multiple opioid or concurrent CNS/sedating medication	According to the Medication coding *(benzodiazepines, sleep aids, muscle relaxant, etc.)
Opioid dosage	According to the Medication coding * (>30mg oral morphine per day or equivalent)
Major organ failure	According to the coding °
Diabetes	if “Yes to Diabetes type I or II”

New Variables§	Derivation

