The predictive risk score for RD, based on the best model selected from analysis above, will be calculated by multiplying each β coefficient taken from the final multivariate model by 10 and rounding to the nearest integer. The integers will then be added together to produce an overall RD risk score for each patient. The resulting continuous distribution of total risk scores across all patients in the derivation set will be then stratified into categories of points (depending on the total sample the quintiles or tertiles or optimal cutoff points) that grouped patients according to the level of risk.

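### The ×10 scoring rule breaks down for continuous predictors and is not tied to the SAP's own mid-value steps, while the planned single cuts on age and BMI discard at least about 36% of that predictor's information

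*SAP*

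**What the plan says.** SAP 7.10.1.1 leaves the scale of the predictors open: "Potential predictors will be reported on continuous scale or grouped into categories". It then lists scoring steps: form categories for each factor (most of them 0/1), choose a reference class, "Calculate mid-values to represent categories", determine the multiplier, and "Determine point score for each risk factor category".

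Further on, the same section gives a different-looking rule. The risk score "will be calculated by multiplying each β coefficient taken from the final multivariate model by 10 and rounding to the nearest integer", after which "The integers will then be added together to produce an overall RD risk score for each patient". Protocol 13.3 also multiplies each coefficient "by 10 and rounding to the nearest integer". Neither statement mentions a unit, a mid-value, a reference class or the patient's own value. The shell of SAP Table 25 has one points cell per predictor, not one per category.

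For age, SAP 7.6 derives "If Age >65 then AGE65=1 otherwise AGE65=0", and it derives obesity in the same way at BMI 30. Protocol 13.1.1 lists both cuts among its 12 predictors. SAP 7.6 also derives AGE50 and BMI35, which match STOP-BANG items.

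**The concern.** The risk score is the primary deliverable, and the text supports more than one way of building it. Two programmers could start from the same fitted model and assign different points to age or BMI. One of those readings, ×10 on a coefficient per year, can give nothing to a predictor that has passed the entry test. Because the form in which age and BMI enter is left open, it could also be settled after the results are known.

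If the single cuts are used instead, the scoring is well defined, but risk is treated as flat on either side of 65 years or BMI 30. That discards information that a linear term would keep at the same cost in degrees of freedom.

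**Working it through.** **Inputs from the documents.** 12 predictors, 10 events per variable, 12% incidence, derivation cohort of 1000 (Protocol 13.1.1, SAP 6); bivariate entry at p ≤ 0.05 (SAP 7.10.1.1); cuts at age 65 and BMI 30 (SAP 7.6).

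**Inputs assumed.** All means, SDs, coefficients and age bands below. The documents give none of them.

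**1. The plan's own figure.** 12 × 10 = 120 events; 120 / 0.12 = 1000. This reproduces. The plan states no point values and no information-loss figure.

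**2. When ×10 gives zero.** round(10 × β) = 0 when |β| < 0.05 per unit, that is, an odds ratio below exp(0.05) = 1.051 per unit, or exp(0.5) = 1.65 per 10 units.

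**3. Can such an effect enter the model?** For small effects, a bivariate test reaches p = 0.05 at about β = 1.96 / [SD × √(N × 0.12 × 0.88)]. With N = 1000 and an assumed age SD of 15, β = 1.96 / (15 × 10.28) = 0.0127 per year. Per-year coefficients from about 0.013 to 0.049 (odds ratio per decade about 1.14 to 1.63) could therefore pass the entry test and earn 0 points. With SD 12 or 18 the lower limit is 0.016 or 0.011.

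**4. Dependence on the unit.** The same effects coded per decade earn more: 0.01 per year becomes 0.1 per decade and 1 point; 0.049 becomes 0.49 and 5 points. Read literally, the integer is also added identically for every patient. Multiplying it by the patient's value would not help, since zero stays zero.

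**5. The two rules side by side.** For a 0/1 factor the mid-value difference is 1, so both give round(10 × β). For age at ×10, with illustrative mid-values 50/65/75/85 and halves rounded up:

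| β per year | Mid-value points | round(10 × β) |
|---|---|---|
| 0.02 | 0/3/5/7 | 0 |
| 0.03 | 0/5/8/11 | 0 |
| 0.04 | 0/6/10/14 | 0 |

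For example, at β = 0.03 the second band scores 10 × 0.03 × 15 = 4.5, rounded to 5.

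**6. Cost of a single cut.** For a normal predictor with a linear logit and a small effect, the information kept is φ(c)² / [p(1 − p)], where c = (cut − mean)/SD and p is the share above the cut.

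| Case (assumed) | Share above | Loss |
|---|---|---|
| Cut at the median | 0.50 | 36% |
| Age 65, mean 60, SD 15 | 0.37 | 39% |
| Age 65, mean 55, SD 15 | 0.25 | 46% |
| Age 65, mean 50, SD 12 | 0.11 | 65% |
| BMI 30, mean 28, SD 6 | 0.37 | 39% |
| BMI 30, mean 24, SD 5 | 0.12 | 63% |

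Simulated logistic models checked this (12% incidence, mean age 58 or 65, SD 15, β 0.02 to 0.05; loss measured by the likelihood-ratio chi-square). One cut at 65 lost 35–40%. Four bands (under 60, 60–69, 70–79, 80 and over), fitted as indicators, lost 13–18%.

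**The case against.** The strongest reply is that the zero-point case is not the planned route. Protocol 13.1.1 and SAP 7.6 define age and BMI as 0/1, the scoring steps begin by forming categories, and the sentence allowing a continuous scale sits in a note to the programmer. The ×10 sentence can be read as supplying the multiplier that the step list leaves to be determined. If bands are fitted as indicators, each has its own β and round(10 × β) works. The step list cites a tutorial on risk-score functions, and SAP 7.6 refers additional or changed derived variables to the Statistical Programming Requirements document; either may fill the gap. Dichotomising also fits the stated aim of a simple tool.

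Much of this stands. Several stronger readings that a reader might infer are not supported:

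- **Every continuous predictor scores zero.** The result depends on the unit and on |β| < 0.05.
- **Age must either score nothing or be reduced to one step.** The SAP's category and mid-value steps already leave room for several bands.
- **The cuts at 65 and 30 are a fallback.** They are the Protocol's planned predictors, chosen from a literature review.
- **The score loses a fixed share, such as 40%, of its information.** The loss is for one predictor and rests on distributions the documents do not give. No effect on the score's ROC area or calibration has been calculated.
- **Age is the strongest predictor.** Protocol 4.1 lists old age among several risk factors without ranking them.

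What the reply does not remove is that the continuous option is in the current text, no sentence links the ×10 rule to the mid-value steps, and Table 25 has no place for points by category.

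**Conclusion.** The point holds in a limited form. For 0/1 factors, the majority, there is no conflict. For a predictor kept on a continuous scale, which the SAP permits, the ×10 rule does not define a usable score. With 1000 patients, 12% events and an assumed age SD of 15, per-year coefficients of about 0.013 to 0.049 could be selected and then score 0.

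Separately, the planned single cuts lose at least about 36% of that predictor's information under normality and a linear logit, and up to about 65% over the means and SDs tried. The 36% floor is a small-effect approximation; simulation gave values as low as 35%. This part concerns efficiency rather than an error in the plan, but it can be remedied within the same 1 degree of freedom. The plan should be changed before the score is derived.

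**What to change.** In SAP 7.10.1.1 and Protocol 13.3, state one rule: points = round[10 × β × (category mid-value − reference mid-value)], which reduces to round(10 × β) for 0/1 factors. Delete the competing wording.

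Enter age and BMI as linear terms. Each uses the same 1 degree of freedom as a cut, so the 10-events-per-variable budget is unchanged. State in advance the bands, the reference band, the mid-values (including a representative value for open-ended bands) and the rounding of halves. Align Protocol 13.1.1 and SAP 7.6 with this coding; AGE50 and BMI35 can remain as STOP-BANG items. Give Table 25 one row per category.

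The cost is some wording and a few more rows in Table 25 and on the score sheet. The approach assumes a linear logit, which should be checked. If the sponsor prefers to keep the single cuts, the minimum change is to remove the continuous option and the mid-value step. That resolves the inconsistency but not the loss of information.

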7.2 General Methodology

At the end of data collection and according to the number of events per variable and number of patients per site, the data-split or the Bootstrap method will be decided. So, all enrolled patients in the MFAS could be randomly assigned to the Derivation Set (DS) and the Validation Set (VS) at a ratio of 2 to 1 or being used all for the derivation and validation. If the method used will be the data-split the randomization will ensure the two cohorts will be not different and they will be compared in terms of baseline characteristics to check possible confounding covariate.

For FAS and PRDPS descriptive statistics will be used to summarize patient characteristics. This will include mean, standard deviation, median, interquartile range, minimum, and maximum for continuous variables, and counts and percentages for categorical variables. It is anticipated that SAS (SAS Institute Inc., Cary, NC, USA) will be used to perform all statistical analyses. Statistical tests will be based on a two-sided significance level of 0.05, and interaction effects evaluated at a significance level of 0.10. Additional exploratory analyses will be conducted as deemed appropriate.

Table 6 - Characteristics of patients in the Derivation and Validation Cohorts– MFAS (if Data-split)

Table 7 - Characteristics of patients – MFAS (if Bootstrap)

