9.1 Measures for model validity

The measures calculated will be:

- The **concordance**: the c statistic. For binary outcomes, c is identical to the area under the receiver operating characteristic (ROC) curve; c varies between 0.5 and 1.0 for sensible models (the higher the better).

- The **calibration slope** is the regression coefficient b in a logistic model with the predictive score as the only covariate: $\text{logit}(\text{mortality}) = a + b * \text{predictive score}$. Well-calibrated models have a slope of 1, while models providing too extreme predictions have a slope less than 1.
- The **Brier score** (or average prediction error) is calculated as $\text{Sum}(y_i - p_i)^2/n$, where y_i denotes the observed outcome and p_i the prediction for subject i in the data set of n subjects.
- The **D statistic** is a scaled version of the model chi-square, which is a function of log-likelihood
- The **R²** as a measure of explained variation.

The table below summarize the three aspects to be checked for model validity:

Aspect	Measure	Characteristics
Calibration	Calibration plot	Visual impression of observed frequencies vs. predicted probabilities
	Slope	Estimate of extremeness of predicted probabilities
	Intercept	Estimate of systematically too high/low predicted probabilities
	E_{avg}	Average absolute difference between observed frequencies and predicted probabilities
	Hosmer-Lemeshow Statistic	Test for 'goodness-of-fit', i.e. deviance of grouped observed outcomes and predicted outcomes
Discrimination	Boxplot of predicted probabilities	Visual impression of spread in predicted probabilities; relies on adequate calibration
	c-statistic (ROC area)	Summary of quality over a range of threshold values
Clinical usefulness (threshold value required)	Accuracy	Percentage of patients correctly classified, given a certain threshold value
	Sensitivity	Percentage of patients with the outcome correctly classified as diseased
	Specificity	Percentage of patients without the outcome correctly classified as non-diseased
	Decrease in weighed false classifications	Model and reference policy are compared by weighing patients falsely classified as diseased and non-diseased according to relative severity

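### Score points and model confidence intervals are taken from unshrunk coefficients after significance-based selection, with no planned correction, and the Adjusted Coefficient column is undefined

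*SAP*

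**What the plan says.** SAP 7.10.1.1 describes the sequence. First comes a bivariate screen: "Independent predictors will be entered in to the model if a significant association, defined as" p ≤ 0.05, with a cap of 0.25 on the correlation between entered predictors. Then: "The multivariate logistic regression model will be performed using a stepwise selection procedure". Protocol 13.3 describes this second step as "using a backward stepwise selection procedure". Neither document gives a stay level. SAP 7.2 sets the general rule: "Statistical tests will be based on a two-sided significance level of 0.05".

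The score "will be calculated by multiplying each β coefficient taken from the final multivariate model by 10 and rounding to the nearest integer", and the integers are summed for each patient. Table 25 is to show bivariate and multivariate odds ratios with 95% confidence intervals, then columns for the coefficient, the "Adjusted Coefficient" and the risk score point. Neither document defines the adjusted column or says whether it feeds the points.

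SAP 7.10.1.1 and 9.2 compute optimism as a difference in performance measures and use it to judge the model. SAP 9.1 lists the calibration slope and notes that "models providing too extreme predictions have a slope less than 1". No step returns that slope, or any other shrinkage, to the coefficients.

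**The concern.** A predictor enters the final model only if its estimate in this sample was large enough to pass the tests. The same estimate then becomes its weight. Among survivors, weak factors are therefore overstated much more than strong ones, so the relative weights are distorted as well as the scale. An interval computed as if the model had been fixed in advance also covers too rarely for those factors.

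The integer score is the trial's main product (the primary objective in both documents). Validation on the split sample or by bootstrap describes how the finished score performs. Even a perfect optimism estimate would leave the published integers, odds ratios and intervals as they are.

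**Working it through.** **The plan's own figures.** 12 variables × 10 events = 120 events; 120 / 0.12 = 1000 derivation patients; 1000 / (2/3) = 1500; 1500 × 1.10 = 1650. These reproduce SAP section 6. The plan gives no figure for coefficient bias or coverage.

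**Inputs.** From the documents: 1000 patients, 12% with RD, 12 candidate predictors, entry at p ≤ 0.05, points = 10β rounded. Assumed: binary predictors with 30% prevalence, independent of one another, a stay level of 0.05, and the true odds ratios (ORs) shown below.

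**Hand check for one predictor.** The information is about 1000 × 0.12 × 0.88 × 0.30 × 0.70 = 22.2, so SE = 1/√22.2 = 0.212. To be kept, |β| must reach 1.96 × 0.212 = 0.416. Any kept factor of this prevalence therefore gets at least about 4 points. A true OR of 1.3 has β = ln 1.3 = 0.262, worth 2.6 points.

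- Its expected z is μ = 0.262 / 0.212 = 1.24.
- P(kept) = P(Z > 1.96) + P(Z < −1.96) = 0.235.
- E[Z | kept] = μ + [φ(1.96 − μ) − φ(1.96 + μ)] / P(kept) = 2.53.
- Expected points when kept = 10 × 2.53 × 0.212 = 5.4, which is 2.05 times the true value.
- The interval covers only if Z lies between 1.96 and μ + 1.96. Given selection, that has probability 0.89.

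**Simulation of the written procedure** (screen, then backward elimination; 1500 samples, 1000 patients each; predictors with ORs from 1.0 to 2.5):

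| True OR | Selected | True points | Mean points when selected | Ratio | CI coverage |
|---|---|---|---|---|---|
| 1.2 | 12% | 1.8 | 5.4 | 2.95 | 74% |
| 1.3 | 21% | 2.6 | 5.5 | 2.08 | 88% |
| 1.5 | 44% | 4.1 | 5.9 | 1.46 | 94% |
| 2.0 | 89% | 6.9 | 7.3 | 1.05 | 98% |
| 2.5 | 99% | 9.2 | 9.3 | 1.01 | 96% |

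Pooled coverage over selected predictors is 92%, and the calibration slope in new patients is 0.84. In the full 12-variable model without selection, coverage is 95% and the mean β at OR 1.3 is 0.262 (unbiased). Its slope is still 0.82, so ending selection does not remove the need for shrinkage.

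**Sensitivity.**
- Three predictors each at OR 1.0, 1.3, 1.5 and 1.8, prevalence 15–40%: 5.4–5.6 points at OR 1.3, pooled coverage 91–92%, slope 0.73–0.74 (0.70–0.76 for the rounded score).
- Latent correlation 0.2: ratio 2.16 and coverage 84% at OR 1.3, pooled coverage 90%, slope 0.89.
- Prevalence 20% or 50%: ratio 2.28 or 2.04 at OR 1.3.
- 1500 patients (180 events) used for derivation: ratio 1.76 and coverage 90% at OR 1.3, pooled coverage 93%, slope 0.88.

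**Where discrimination is lost** (second set of effects). The planned score has c = 0.606. Giving the same selected variables their true weights raises c to 0.611. True weights on all 12 give 0.645. Of the 0.039 lost, 0.005 comes from the weights and 0.034 from discarded predictors.

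**The case against.** Four stronger readings are tempting, and the documents do not support them.

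First, that weak factors get about twice their true points. This holds only near an assumed OR of 1.3 and only when the factor is selected. Counting the zeros, such a factor averages 21% × 5.6 = 1.2 points against a true 2.6, so over repeated samples it is under-weighted.

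Second, that the reported 95% intervals under-cover generally. Under-coverage is marked only for weak factors. From OR 1.5 upward, coverage is close to nominal or above it. A null predictor that survives cannot be covered, by construction. The bivariate intervals, which 7.10.1.1 plans for each potential predictor, are unaffected if all candidates are shown.

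Third, that the adjusted column is not used for the score. If adjusted means multivariable-adjusted, that column is the source of the points. If it means optimism-adjusted, the scoring rule bypasses it. The SAP also sends some derivation details to a programming requirements document that is not available here. What can be said is that the column needs a definition.

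Fourth, that inflated points put patients in the wrong risk group. Groups cut at quantiles do not depend on the overall scale of the score. With true weights on the selected variables, disagreement with the true top third fell only from 22% to 20%.

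It is also fair to say that overfitting would be seen: SAP 9.1 plans the slope, intercept, Brier score and calibration plot. These points limit the size of the problem. They do not supply the missing correction.

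**Conclusion.** The concern holds in a limited form. The SAP takes the points and the multivariate intervals from a model chosen by significance testing on the same data, and plans no correction for either. The direction follows from the written rule. The size rests on assumed odds ratios, prevalences and stay level.

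Under those assumptions, a surviving weak factor is overstated about 3-fold at OR 1.2, 2-fold at 1.3 and 1.5-fold at 1.5, with almost no overstatement by 2.0. Interval coverage is about 86–88% at OR 1.3 and 91–92% pooled, a little lower if predictors are correlated. The slope in new patients is about 0.7–0.85 with independent predictors and nearer 0.9 with the correlation tried. Deriving the score on 1500 patients reduces the problem but does not remove it. Most of the loss in discrimination comes from dropping predictors, not from inflated points. The change is worth making before analysis; the concern does not invalidate the study.

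**What to change.** 1. In SAP 7.10.1.1, fit the 12 predictors listed in protocol 13.1.1 with a ridge-penalised logistic model, the penalty chosen by cross-validation. Define the Adjusted Coefficient as that coefficient, set points = round(10 × Adjusted Coefficient), and re-estimate the intercept. In 120 simulated samples under the second set of effects, ridge gave a slope of 1.04.

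2. In Table 25, give odds ratios and 95% confidence intervals from the unselected 12-predictor model. Label any selected-model intervals as not accounting for selection.

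3. If selection is kept, repeat both the screen and the stepwise step in each of the 500 bootstrap replicates. SAP 9.2 mentions univariate and multivariate models in each replicate, while 7.10.1.1 mentions only the multivariate one, so this needs stating. Multiply the coefficients by the bootstrap calibration slope. State that this corrects overall calibration only, not the relative weights or the quantile risk groups: with a factor of 0.84, OR 1.3 falls from 5.5 to 4.6 points (true 2.6), while OR 2.5 falls from 9.3 to 7.8 (true 9.2).

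The cost is SAP wording and modest extra programming, with no new data. The downsides are a score with more items and smaller published points and odds ratios.
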